#### 7.1.7 Excluded Treatments, Medical Devices, and/or Procedures During Study Period

The following medications are not permitted throughout the 3 on-study cycles:

- Commercially available romiplostim (Nplate®)
- Other thrombopoietic receptor agonists (eg, eltrombopag [Promacta® or Revolade®], avatrombopag [Doptelet®])
- Recombinant human TPO
- Oprelvekin (Neumega®)
- Herbal supplements that are associated with bleeding side effects including, but not limited to, gingko biloba, garlic, ginseng, fish oil, dong quai, feverfew. Garlic and ginseng taken through a normal diet would not be excluded.
- Any other investigational agents that are not approved
- Subjects must not schedule any elective surgeries during the treatment period and for at least 28 days after the last administration of investigational product. If a subject undergoes any urgent surgery during the course of the study, investigational product must be withheld and the investigator or designee should notify the sponsor's medical monitor as soon as possible. A subject may be allowed to resume investigational product if both the investigator and sponsor's medical monitor agree to restart study therapy.

## 7.2 Method of Treatment Assignment

Subjects will be randomized in 2:1 allocation ratio, to romiplostim or placebo, respectively, in double-blind manner.

The randomization number will be provided by the IVRS/IXRS system.

The randomization will be stratified by tumor type and baseline platelet count ( $< 50 \times 10^9/L$ ,  $\geq 50 \times 10^9/L$ ). Gastrointestinal tract cancers, including tumors of the esophagus or stomach, will be included in one stratum, pancreatic cancers will be included in a second stratum, and colorectal cancers, including tumors of the colon or rectum, will be included in a third stratum.

The randomization date is to be documented in the subject's medical record and on the enrollment CRF.

## 7.3 Blinding

This is a double-blind study. Treatment assignment will be blinded to all subjects, site personnel, and Amgen as described below.

### 7.3.1 Site Personnel Access to Individual Treatment Assignments

A subject's treatment assignment is to only be unblinded when knowledge of the treatment is essential for further clinical management of the subject on this study. Unblinding at the study site for any other reason will be considered a protocol deviation. Unblinding is done via IVRS. The Amgen Trial Manager must be notified before the blind is broken unless identification of the study treatment is required for a medical emergency in which the knowledge of the specific blinded study treatment will affect the immediate management of the subject's condition. In this case, the Amgen Trial Manager must be notified within 24 hours after breaking the blind. The date and reason that the blind was broken must be recorded in the source documentation and CRF, as applicable.

### 7.3.2 Access to Individual Subject Treatment Assignments by Amgen or Designees

Blinded individuals will not have access to unblinded information until the study is formally unblinded. Unblinding and potentially unblinding information is not to be distributed to the study team, investigators or subjects prior to the study being formally unblinded except as specified (eg, Section 7.3.1).

## 7.4 Dose Modification

### 7.4.1 Dosage Adjustments, Delays, Rules for Withholding or Restarting, Permanent Discontinuation

#### 7.4.1.1 Amgen Investigational Product: Romiplostim and Placebo

Each subject's dose of investigational product (romiplostim or placebo) will be adjusted based on weekly platelet counts (see [Table 7-1](#)). **The target platelet count at initiation of the first on-study cycle of chemotherapy is  $\geq 100 \times 10^9/\text{L}$ . Starting from week 4, subjects may start the first cycle of chemotherapy with dose adjustments according to the dose modification guidelines listed below.**

If there are multiple platelet values performed on a study visit date, the platelet value from the test performed most immediately prior to the time of the planned investigational product and/or non-investigational product administration will be recorded as the platelet value for that study visit date and will be used to determine the subject's dose of investigational product and, when applicable, chemotherapy dose modifications, which include dose reductions, delays, omissions, and discontinuation. Local laboratory assessments taken during the study visit ( $\pm 1$  day) and recorded in the CRF must be the same values as used for investigational product dose calculations and chemotherapy dose modifications where applicable. **Any platelet counts performed in the cycle prior to enrollment should be recorded if they are used to determine chemotherapy dose in study cycle 1. Any platelet counts performed outside of the study visits should be recorded if they are used to determine chemotherapy dose in study cycles 1, 2, and 3.**

**Table 7-1. Investigational Product Dose Adjustment Rules**

Platelet count ( $\times 10^9/\text{L}$ )	Investigational Product Dose Adjustment Rule a
< 100	Increase dose by 1 $\mu\text{g}/\text{kg}$ each week (to a maximum of 10 $\mu\text{g}/\text{kg}$ )
100 - 250	Dose remains constant
251 - 450	Dose reduced by 1 $\mu\text{g}/\text{kg}$ . Do not withhold dose b, c
> 450	Withhold dose d

IP = investigational product

a The starting dose of investigational product will be 2  $\mu\text{g}/\text{kg}$  based on the subject's recorded screening weight. See Section [7.1.1.2](#) for full details.

b If the current dose is 1  $\mu\text{g}/\text{kg}$  and a dose reduction is required, the dose will be withheld until the platelet count falls to  $< 100 \times 10^9/\text{L}$ . Once the platelet count is  $< 100 \times 10^9/\text{L}$ , dosing will resume at a dose of 1  $\mu\text{g}/\text{kg}$  using the dose adjustment rules above.

c If platelet count  $> 250 \times 10^9/\text{L}$  is due to a platelet transfusion in the preceding 7 days, the subject will continue to receive investigational product at the previous dose level.

d For patients who previously had their dose withheld because their platelet count was  $> 450 \times 10^9/\text{L}$ , restart IP based on dose withheld and according to adjustment rules above.

Subjects who have a platelet count  $< 100 \times 10^9/L$  for 4 consecutive weeks at the maximum investigational product dose of 10  $\mu g/kg$  should be discontinued from investigational product, **allowing for up to 12 weeks of dosing before a subject is declared a non-responder**. To assess if a subject has responded to the 12th dose given at the beginning on the 12th week of the study, the platelets would be drawn a week later at the week 13 visit when a subject has completed 12 weeks of dosing.

Dosing will be discontinued at any time during the study if neutralizing antibodies to romiplostim or to endogenous TPO are detected.

The reason for dose change of investigational product is to be recorded on each subject's CRF(s).

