#### **3.3.3.2 Thrombotic/Thromboembolic Complications**

Thrombotic complications, which can represent one of the earliest signs of cancer, occur at a higher rate in cancer patients than in the general population and have important implications for treatment and quality of life (Clagett et al, 1988; Cronin-Fenton et al, 2010; Prandoni et al, 2002; Shen et al, 1980; White et al, 2005). Most commonly, these events are deep vein thrombosis (DVT) or pulmonary embolism, which are both forms of venous thromboembolism (VTE). Arterial events, such as stroke and myocardial infarction occur less commonly (Falanga, 2005). Venous thromboembolism is also associated with increased mortality in cancer patients (Khorana et al, 2006; Lyman,

2011). Chemotherapy agents most strongly correlated with thrombotic complications are platinum (8% to 18%), such as cisplatin or carboplatin, asparaginase (4% to 14%), fluorouracil (15% to 17%), and antiangiogenic agents, such as thalidomide and lenalidomide (Kroger et al, 2006). Cisplatin, in particular, is correlated with a 12% to 18% risk of strokes, recurrent peripheral arterial events, and aortic thrombosis (Numico et al, 2005). Research has consistently shown that chemotherapy treatment significantly increases the risk of thromboembolic events (Haddad and Greeno, 2006; Kyriazi and Theodoulu, 2013; Lyman, 2011).

In addition to the increased risk of VTE in this patient population, romiplostim treatment is expected to increase the number of circulating platelets and platelet counts above the normal range and thus carries a theoretical risk for thrombotic/thromboembolic complications. These complications have a high patient impact and any clinical sequelae (eg, stroke) may not be reversible. In this study, subjects with platelet counts  $> 450 \times 10^9/L$  will have investigational product withheld, with treatment re-initiated when platelet counts are  $\leq 450 \times 10^9/L$  (refer to Section 7.4.1.1 for dosage adjustments).

In the retrospective review of romiplostim for use for dose-limiting CIT (Parameswaran et al, 2014), the safety data showed 3 of 20 subjects experienced DVT, which would not be unexpected in this patient population. Three of 51 subjects in the phase 1/2 IIS (NCT00147225 Vadhan-Raj et al, 2009), in subjects with solid tumors treated with romiplostim, experienced a thromboembolic event (2 subjects with pulmonary embolism and 1 subject with DVT).

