**7.7 Treatment of Overdose**

In high-dose preclinical studies, the noted effects were related to the pharmacological action of romiplostim. Overdose may result in an excessive increase in platelet counts associated with thrombotic/thromboembolic complications. In the event of an investigational product overdose, platelet counts should be monitored frequently and investigational product dose withheld if platelet counts are > 450 x 10^9/L. Reinitiate treatment with investigational product when platelet counts are ≤ 450 x 10^9/L and refer to Section 7.4.1.1 for dosage adjustments.

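### Protocol Table 7-1 and Sections 3.3.3.2 and 7.7 give opposite instructions on investigational product in two situations: a transfusion-related count above 450, and a fall from above 450 to 251-450 at 1 µg/kg

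*Protocol*

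**What the plan says.** All counts are in 10^9/L.

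- **Table 7-1, 251-450 row** (Protocol Section 7.4.1.1): reduce by 1 µg/kg and do not withhold. Footnotes b and c are marked here.
- **Footnote b:** if the current dose is 1 µg/kg "and a dose reduction is required, the dose will be withheld until the platelet count falls to" below 100.
- **Footnote c:** if a count above 250 is due to a platelet transfusion in the preceding 7 days, "the subject will continue to receive investigational product at the previous dose level". No upper limit is given.
- **Table 7-1, above-450 row:** withhold. Only footnote d is marked here.
- **Footnote d:** after a hold for a count above 450, "restart IP based on dose withheld and according to adjustment rules above". No restart count is given.
- **Section 3.3.3.2:** subjects with counts above 450 "will have investigational product withheld, with treatment re-initiated when platelet counts are" 450 or lower, with a referral to Section 7.4.1.1 for dosage adjustments. It makes no exception for transfusion.
- **Section 7.7** (after an overdose): withhold above 450, then "Reinitiate treatment with investigational product when platelet counts are" 450 or lower, with the same referral.

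**The concern.** Section 7.1.1.2 bases dose adjustments on platelet counts only, so these rules decide what a subject receives each week. Two investigators who both follow the protocol could act differently on the same count: one gives the dose and the other withholds it.

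The protocol itself treats this as a sensitive area. Section 3.3.3.1 lists medication errors as a key risk and says that small dose differences may have large effects on counts. Section 3.3.3.2 lists thrombosis as a key risk and gives the above-450 rule as the safeguard. Opposite instructions at that boundary weaken the safeguard. They also leave no fixed standard for judging a dose as compliant (SAP Section 9.3) or for interpreting the reasons for omitted doses tabulated under SAP Section 9.6.6.

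**Working it through.** The plan states no figure to reproduce here. The check sets the rules side by side and then applies them to assumed counts, because the documents give no platelet trajectories.

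**Situation 1: a transfusion-related count above 450, at any dose.** Take a count of 500 due to a transfusion within the preceding 7 days.

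| Rule | Condition met? | Action |
|---|---|---|
| Footnote c | yes, 500 > 250 and transfusion-related | continue at the previous dose |
| Above-450 row | yes, 500 > 450 | withhold |
| Section 3.3.3.2 | yes, 500 > 450 | withhold |

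The position of the footnote marker suggests that c was meant for 251-450 only. The words of the footnote do not say so. The two actions cannot both be taken.

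**Situation 2: a subject at 1 µg/kg whose count falls from above 450 to 251-450.** Assumptions: weekly counts of 500, 300, 200, 150, 120 and 90, no missed visits and no transfusion.

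- *Rule I, Sections 3.3.3.2 and 7.7 taken at their words:* product restarts at the first count of 450 or lower. I assume that the dose given is 1 µg/kg, because subtracting 1 from 1 leaves nothing to give.
- *Rule II, following the referral to Section 7.4.1.1:* footnote d applies the table to the withheld dose. At 300 the 251-450 row calls for a reduction from 1 µg/kg, so footnote b withholds until the count is below 100.

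| Week | Count | Rule I | Rule II |
|---|---|---|---|
| 1 | 500 | held | held |
| 2 | 300 | given | held |
| 3 | 200 | given | held |
| 4 | 150 | given | held |
| 5 | 120 | given | held |
| 6 | 90 | given | given |
| **Doses held** | | **1** | **5** |

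The difference is 5 - 1 = 4 weekly doses on this path.

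**Limits of situation 2.** Two variations show where the conflict stops:

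- At 1 µg/kg with counts 500, 200, 180, 150, 120, 90, the count skips the 251-450 band. Both rules hold 1 dose.
- At 2 or 3 µg/kg with counts 500, 300, 200, 150, 120, 90, a reduction is possible without reaching zero. Both rules hold 1 dose.

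The conflict therefore needs both a dose of 1 µg/kg and a restart count in 251-450.

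**The case against.** The strongest reply is that Sections 3.3.3.2 and 7.7 supplement the table. Footnote d gives no restart count, the two sections supply one, and both send the reader to Section 7.4.1.1 for the adjustment. For most subjects this works: the sections agree with each other and with the above-450 row. It fails for the subject in situation 2, where the referral leads to an instruction not to restart. A reader can take the referral as settling only the dose, or as settling whether to dose at all. For situation 1, the reply is that footnote c's marker limits it to its own row. That is a reasonable inference, but the footnote's stated condition is wider than the row.

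Both situations may also be uncommon. Section 3.2.1 says that transfusions are usually reserved for bleeding or counts below 10. This bears on priority but does not remove the contradictions.

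A reader might infer more from the same table, and the documents do not support it:

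- *That a mild overshoot at 1 µg/kg wrongly stops product for longer than a count above 450.* Where this happens it follows from footnote b alone. The rule is determinate and a clinical design choice, and the longer hold does not occur on every path.
- *That "Do not withhold dose" contradicts footnote b.* The footnote is a marked exception to those words, for the one dose at which a reduction leaves nothing to give.
- *That the restart dose under footnote b could be 1 or 2 µg/kg.* The footnote says "dosing will resume at a dose of 1" µg/kg. The mention of the adjustment rules reads naturally as later titration.
- *That footnote d is in conflict at counts below 100.* Applying the table to the withheld dose gives one answer.

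**Conclusion.** Two contradictions stand. Footnote c continues dosing at a transfusion-related count above 450, where the above-450 row and Section 3.3.3.2 withhold. At 1 µg/kg with a count falling from above 450 to 251-450, Sections 3.3.3.2 and 7.7 re-initiate, while footnotes d and b withhold until below 100. On the one assumed path this is 1 dose held against 5. That figure illustrates the gap and does not estimate a typical effect, since it depends on the path and on the assumed restart at 1 µg/kg.

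The frequency of either situation is unknown. No sample size, power or alpha figure changes. A reader might also infer that interruptions in responders pull the treatment effect toward the null, citing the 59% in one retrospective series who responded after a single dose (Section 3.2.4.2). That figure counts subjects reaching at least 100, not above 250, in a series with a median starting dose of 3 µg/kg. It says nothing about how often these rules would be triggered at this trial's starting dose of 2 µg/kg, and the documents offer nothing else from which to estimate an effect on the primary endpoint.

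**What to change.** The sponsor's medical team should reconcile Table 7-1, footnotes b to d and Sections 3.3.3.2 and 7.7 so that each situation has one stated action:

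1. For a transfusion-related count above 450, state whether footnote c or the above-450 row governs, and make Section 3.3.3.2 agree.
2. For a subject at 1 µg/kg whose count falls from above 450 to 251-450, state whether product is restarted or withheld, and at what count and dose it resumes. Use the same statement in footnotes b and d and in Sections 3.3.3.2 and 7.7.

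The choice of action is the medical team's, and this review does not propose one. The cost is a protocol wording change and a matching update to the dosing worksheet, with no added procedures or subjects.

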#### **7.4.1.2 Non-Amgen Non-investigational Product: Standard-of-care Chemotherapy**

The following will be specified prior to the first administration of investigational product: chemotherapy agents in the planned treatment regimen, planned total dose and unit of each agent, number of days per cycle, and planned dosing schedule. The planned chemotherapy regimen reflects what the investigator considers standard dose and schedule for that regimen. The following will be captured during the treatment period: the actual chemotherapy dose and unit administered; date of administration; whether the subject experienced a dose reduction, delay, or omission due to thrombocytopenia; whether the subject experienced chemotherapy treatment discontinuation due to thrombocytopenia; and whether there was a reason other than thrombocytopenia for dose reduction, delay, omission, or discontinuation. An independent adjudicator will periodically verify the reason for chemotherapy dose modification in the study.

Chemotherapy dose modifications include dose reductions, dose delays, dose omissions, and treatment discontinuations. During the 3 on study cycles, a chemotherapy delay must be increments of 1 week to align with the weekly study visits if applicable.

Following enrollment and initiation of investigational product, the first cycle of chemotherapy during the treatment period should not be administered until platelet counts are  $\ge 100 \times 10^9/L$  or until **at least** week 4, whichever occurs first. **If platelet counts at the start of chemotherapy cycle 1 are  $< 100 \times 10^9/L$ , recheck platelet count 1 week later and continue to hold until platelet count  $\ge 100 \times 10^9/L$ . Starting from week 4, subjects may start the first cycle of chemotherapy with dose**

adjustments according to the dose modification guidelines listed below. If the platelets remain  $< 100 \times 10^9/L$ , the investigator has the discretion to continue IP for dose escalation up to 12 weeks before beginning the first on-study chemotherapy cycle. After 12 weeks without starting study cycle 1 on IP, the subject is considered a non-responder.

**Do not start the first cycle of on-study chemotherapy before study week 2.** The start of the planned chemotherapy must be no more than 2 days after the local laboratory assessments have been taken **during the study visit**. The reason for dose change of non-Amgen non-investigational products is to be recorded on each subject's CRF(s). Any chemotherapy dose modifications made for reasons other than thrombocytopenia will be captured in the CRF.

**The investigator should not perform any dose modifications due to CIT if the subject's platelet count is above the levels listed in the dose modification guidelines. Do not dose modify for cycle 1 unless the platelets are  $< 100 \times 10^9/L$  on or after week 4. Use dose modification guidelines for cycles 2 and 3.**

Chemotherapy dose modifications for thrombocytopenia for patients with gastric, esophageal, pancreatic, colon, or rectal adenocarcinoma receiving an oxaliplatin-based regimen should be conducted as follows.

**Table 7-2. Dose Modification Based on Platelet Counts—mFOLFOX6**

Blood Counts	Delay Cycle	Oxaliplatin	5-FU
Platelets $< 75 \times 10^9/L$ day 1 (at the beginning of a chemotherapy cycle)	Delay by 1 week and until platelets have recovered $\geq 75 \times 10^9/L$ .		
	1 st occurrence of a 2 week delay or delay for 1 week on 2 separate occasions		Eliminate 5-FU bolus If no bolus was given reduce cIV 5-FU by 20%
	2 nd Occurrence of a 2 week delay or delay for 1 week on 2 separate occasions	Reduce oxaliplatin dose from 85 to 65 mg/m 	Reduce cIV 5-FU by 20%
Platelets $< 50 \times 10^9/L$ during treatment	Delay next dose until platelets recover to $\geq 75 \times 10^9/L$ .	Reduce oxaliplatin dose to 75 mg/m  (adjuvant therapy) or to 65 mg/m  (metastatic CRC)	

5-FU = 5-fluorouracil; cIV = continuous intravenous; CRC = colorectal cancer  
Source: Oxaliplatin USPI; Cheeseman et al, 2002; Hochster et al, 2008.

**Delay treatment cycle by one week for platelets < 75 x 10^9/L on the day 1 of treatment. If treatment is delayed for 2 weeks or delayed for one week on 2 separate occasions, eliminate 5-FU bolus. If no bolus was given reduce cIV 5-FU by 20%. With the second occurrence, reduce cIV 5-FU by 20% and reduce oxaliplatin dose from 85 to 65 mg/m^2. For platelets <50 x 10^9/L during treatment delay next dose until platelets recover to ≥ 75 x10^9/L then reduce oxaliplatin dose to 75 mg/m^2 (adjuvant therapy) or to 65 mg/m^2 (metastatic CRC).**

**Table 7-3. Dose Modification Based on Platelet Counts - FOLFIRINOX**

Blood Counts	Delay Cycle	Oxaliplatin	5-FU	Irinotecan
Platelets < 75 x 10  /L day 1 (at the beginning of a chemotherapy cycle)	Delay by 1 week and until platelets have recovered ≥ 75 x10  /L.	Reduce oxaliplatin dose from 85 to 60 mg/m 	Reduce bolus and cIV 5-FU to 75% of original dose	
				2 nd Occurrence: reduce dose to 150 mg/m 
Platelets < 50 x 10  /L during treatment		Reduce oxaliplatin dose from 85 to 60 mg/m 	Reduce bolus and cIV 5-FU to 75% of original dose	
			2 nd Occurrence: reduce cIV 5-FU an additional 25%	2 nd Occurrence: reduce dose to 150 mg/m 

5-FU = 5-fluorouracil; cIV = continuous intravenous

Source: Conroy et al, 2011.

**If day 1 treatment delayed by 1 week for platelet count < 75 x 10^9/L, reduce oxaliplatin dose from 85 to 60 mg/m^2 and reduce both the bolus and cIV 5-FU to 75% of original doses. For second occurrence, reduce irinotecan dose to 150 mg/m^2. Beginning in on-study chemotherapy cycle 2 if nonrecovery after 2-week delay, or third occurrence of platelets < 75 x 10^9/L, discontinue treatment. For platelet count < 50 x 10^9/L during treatment, reduce oxaliplatin dose from 85 to 60 mg/m^2 and the cIV 5-FU dose to 75% of the original dose. For the second occurrence, reduce dose of irinotecan to 150 mg/m^2 and the dose of cIV 5-FU an additional 25%. Discontinue treatment for third occurrence.**

Table 7-4. Dose Modification Based on Platelet Counts - mFOLFIRINOX

Blood Counts	Delay Cycle	Oxaliplatin	5-FU	Irinotecan
Platelets < 75 x 10  /L day 1 (at the beginning of a chemotherapy cycle)	Delay by 1 week and until platelets have recovered ≥ 75 x10  /L.	Reduce oxaliplatin dose from 85 to 60 mg/m 	Reduce cIV 5- FU to 75% of original dose	
				2 nd Occurrence: reduce dose to 120 mg/m 
Platelets < 50 x 10  /L during treatment		Reduce oxaliplatin dose from 85 to 60 mg/m 	Reduce cIV 5-FU to 75% of original dose	
			2 nd Occurrence: reduce cIV 5-FU an additional 25%	2 nd Occurrence: reduce dose to 120 mg/m 

5-FU = 5-fluorouracil; cIV = continuous intravenous

Source: Conroy et al, 2018

If day 1 treatment delayed by 1 week for platelet count <75 x 10^9/L, reduce oxaliplatin dose from 85 to 60 mg/m^2 and reduce the cIV 5-FU to 75% of original doses. For second occurrence, reduce irinotecan dose to 120 mg/m^2. Beginning in on-study chemotherapy cycle 2 if nonrecovery after a 2-week delay, or if there is a third occurrence of platelets <75 x 10^9/L, discontinue treatment. For platelets < 50 x 10^9/L during treatment, reduce oxaliplatin dose from 85 to 60 mg/m^2 and the infusional FU dose to 75% of the original dose. For the second occurrence, reduce dose of irinotecan to 120 mg/m^2 and the dose of infusional FU an additional 25%. Discontinue treatment for third occurrence.

The dose modifications for the FOLFOXIRI regimen in colorectal cancer patients were not published in the original phase III trial (Falcone et al, 2007). Use the dose modifications above based on those in a trial using a comparable regimen (FOLFIRINOX) for advanced pancreatic cancer (Conroy et al, 2011).

For CAPEOX (Nehls et al, 2008; Capecitabine USPI), delay the treatment cycle for one week if the platelet count is < 100 x 10^9/L on day 1. If treatment is delayed for 2 weeks or delayed for 1 week on 2 separate occasions, reduce the doses of oxaliplatin and capecitabine by 10% to 20%. Subsequent treatment cycles should be delayed until the platelets are ≥ 75 x 10^9/L.

Renal insufficiency requiring dose modification

- For patients with severe renal impairment (creatinine clearance < 30 mL/min), the starting dose of oxaliplatin should be reduced to 65 mg/m^2 (Oxaliplatin prescribing information, 2017).
- Decrease the dose of capecitabine by 25% in patients with CrCl 30-50 mL/min and hold for more severe kidney disease. (Xeloda USPI 2019)
- For irinotecan there is no specific dose reduction recommendation for renal insufficiency. (Irinotecan USPI)

Hepatic insufficiency requiring dose modification

- For patients with hepatic impairment with total bilirubin > 5 mg/dL, 5-fluorouracil should not be administered (Floyd et al, 2006). Decrease the dose of capecitabine by 25% in subsequent cycles for bilirubin > 1.5-3 x ULN. (Blum, 1999)
- The dose of irinotecan should be reduced by 25% in patients with bilirubin > 1.5-3 x ULN. (Floyd 2006).

Where there are multiple toxicities including thrombocytopenia, renal, and hepatic toxicities dose modification should be made after reviewing all applicable dose modification guidelines provided and choosing the lowest recommended dose for the most severe grade of toxicity.

